5.3.9. Blinding and Unblinding

This is a randomized, double-blind study.

The subject, the investigator, the study coordinator, the sponsor and the entire study processing team will remain blinded to treatment assignment. The blind can be broken only if the investigator deems it is necessary for the safe treatment of a subject. The investigator is encouraged to discuss considerations to break the blind with the medical monitor whenever possible and where the situation allows, and to inform the sponsor. However, the investigator is responsible for the medical care of the individual trial subject and the responsibility to break the treatment code in emergency situations resides solely with the investigator. The investigator is not required to discuss unblinding if he or she feels rapid emergency unblinding is necessary.

If the blind is broken for any reason during the course of the study, the moment at which the subject’s data were unblinded and all other relevant information will be documented by the clinical study center, CRO, and other sponsor designees, as appropriate. The reason for breaking the blind will be indicated and justified in the source documentation and in the eCRF. The blind can be broken by the investigator via the IWRS.

All subjects who are unblinded while on the study will be withdrawn at the moment of unblinding, with the reason for unblinding given as the reason for discontinuation from the

study. If an AE leads to unblinding, the AE must be given as the reason for unblinding and the AE must also be recorded in the eCRF. All subjects who are unblinded must, where possible, complete the ED visit. Any AEs must be followed until resolution or until stabilization.

6. STUDY ASSESSMENTS

6.1. TIMING OF ASSESSMENTS

The study assessments described below will be performed at the time points specified in the flow chart in Section 1. All assessments should be performed pre-dose. In addition, some assessments are also to be performed at defined time points post-dose when specifically mentioned. The procedures listed below must be performed in the following order:

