1. STUDY FLOW CHART

The schedule of assessments is given in the flow chart below.

EVENT	SCREENING	TREATMENT PERIOD ¹				FOLLOW-UP
		D1	D15 (±2D)	D29 (±2D)	ED	
Study days (D)	D-28 till D-1					
Informed consent ²	X					
Inclusion/exclusion criteria	X	X				
CFQ-R ³	X	X	X	X	X	X
Demographics	X					
Medical history	X					
Physical examination ⁴	X	X	X	X	X	X
Weight	X	X	X	X	X	X
Vital signs ⁵	X	X	X	X	X	X
Pulse oximetry ⁶	X	X	X	X	X	X
12-lead ECG ⁷	X	X	X	X	X	X
Sweat collection	X	X	X	X	X	X
Spirometry ⁸	X	X	X	X	X	X

¹ All assessments are to be performed pre-dose. In addition, some assessments are also to be performed at defined time points post-dose when specifically mentioned.

² Written informed consent to be obtained before any study-related procedures and/or assessments are performed.

³ CFQ-R to be completed prior to any other assessments scheduled for that visit.

⁴ Full physical examination at screening (including height); limited physical examination (ear, nose, throat, chest and neck) at subsequent visits.

⁵ Vital signs include heart rate, blood pressure (systolic and diastolic), respiratory rate and oral body temperature. Heart rate and blood pressure to be captured after 5 minutes in supine position. Vital signs must be recorded pre-dose at all visits, and additionally between 3 and 4 hours post-dose on Day 1.

⁶ Pulse oximetry to determine oxygen saturation is to be captured after at least 5 minutes of rest in seated or supine position.

⁷ 12-lead ECG to be measured after at least 5 minutes of rest in supine position.

⁸ Spirometry must be performed pre-dose at all visits, and additionally between 1 and 2 hours post-dose on Day 1 and Day 29.

CFQ-R = Cystic Fibrosis Questionnaire - Revised; ECG = electrocardiogram; ED = early discontinuation

EVENT	SCREENING	TREATMENT PERIOD ¹				FOLLOW-UP
		D1	D15 (±2D)	D29 (±2D)	ED	
Study days (D)	D-28 till D-1					
Clinical safety laboratory tests ⁹	X	X	X	X	X	X
Serology ¹⁰	X					
Pregnancy test ¹¹	X	X		X	X	X
FSH test ¹²	X					
CFTR genotyping		X				
PK blood samples ¹³			X	X	X	
Exploratory biomarkers ¹⁴		X	X	X		
Randomization		X				
Breakfast or snack to be provided ¹⁵		X	X	X		
Study drug dosing						
Study drug dispensing		X	X			
Dispense subject diary	X	X	X	X		
Collect subject diary		X	X	X	X	X
AE assessment						
Concomitant medications						
Optional substudy¹⁶						
Nasal brushing		X	X	X		

⁹ Blood and urine samples to be collected for clinical safety laboratory tests.

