2.5. CLINICAL INVESTIGATION

2.5.1. GLPG2222-CL-101

GLPG2222 or placebo has been administered during the single ascending dose and multiple ascending dose parts of the first-in-human study GLPG2222-CL-101 in healthy male subjects. Part 1 (single ascending dose) consisted of 2 cohorts of 8 subjects (total of 16 subjects) who sequentially received a single dose of [REDACTED] study drug in Cohort A, and a single dose of [REDACTED] study drug in Cohort B in a placebo-controlled, double-blind, alternating panel manner. Subjects received the study drug in a 3:1 randomized balanced fashion so that per dose level, 6 subjects received GLPG2222 and 2 subjects received placebo. Part 2 (multiple ascending dose) consisted of 3 consecutive cohorts of 8 subjects (total of 24 subjects). Subjects in Cohort C received oral doses of [REDACTED] GLPG2222 or placebo q.d. for 14 days, subjects in Cohort D received oral doses of [REDACTED] GLPG2222 or placebo q.d. for 14 days, and subjects in Cohort E received oral doses of [REDACTED] GLPG2222 or placebo q.d. for 14 days. Subjects received the study drug in a 3:1 randomized balanced fashion so that per dose level, 6 subjects received GLPG2222 and 2 subjects received placebo.

Pharmacokinetics

GLPG2222 given as oral suspension in fed state was rapidly absorbed with a median time to occurrence of C_{max} (t_{max}) range of [REDACTED] and was eliminated with a mean [REDACTED]. After q.d. dosing for 14 days, steady-state exposure (both C_{max} and AUC for the dosing interval) increased in proportion to the dose within the [REDACTED] mg dose range and more than dose-proportionally within the [REDACTED] dose range.

Steady state in GLPG2222 plasma concentrations was reached after 2 dosing days with a minimal accumulation (1.5). Less than 0.1% of GLPG2222 was excreted in urine.

Urinary 6- β -OH-cortisol/cortisol ratio was not impacted by q.d. repeated dosing, suggesting that GLPG2222 is not a CYP3A4 inducer.

Safety

There were no deaths or serious adverse events (SAEs) reported during the study, all treatment-emergent adverse events (TEAEs) were mild in intensity. All but one TEAE were resolved at the end of the study. One TEAE was reported as not recovered at the end of the study (600 mg q.d., nasopharyngitis) and was considered not related to the study drug by the investigator. Headache was the most common TEAE. There was no evidence of a dose-response relationship for any TEAE.

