4. STUDY ENDPOINTS

4.1. PRIMARY ENDPOINT

- Safety and tolerability, assessed by the incidence of adverse events (AEs), as well as changes over time in weight, vital signs, oxygen saturation by pulse oximetry, 12-lead ECG, spirometry, and clinical safety laboratory data (hematology, chemistry, coagulation and urinalysis).

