6.4.4. Oxygen Saturation by Pulse Oximetry

Arterial oxygen saturation by pulse oximetry will be measured at the time points specified in the flow chart. Pulse oximetry will be collected after the subject has been at rest (seated or supine) for at least 5 minutes.

Normal ranges for pulse oximetry are presented in Appendix 2. Any clinically relevant abnormalities should be reported as AEs.

6.4.5. 12-lead ECG

A resting 12-lead ECG will be recorded at the time points specified in the flow chart. Subjects should rest for at least 5 minutes in supine position prior to ECG evaluation. Parameters to be recorded include the following: HR, RR interval, PR interval, QRS, uncorrected QT interval, morphology, and rhythm analysis. QTcF will be calculated during the statistical analysis.

Normal ranges for ECG parameters are presented in Appendix 2. ECGs will be interpreted by the investigator for clinical significance. Any clinically relevant abnormalities should be reported as AEs.

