6.5. PHARMACOKINETICS ASSESSMENTS

6.5.1. Blood Samples

Blood samples will be collected during the treatment period for the determination of GLPG2222 in plasma at the following time points:

- Day 15: pre-dose and 0.5, 1, 2, 3, 4, 6 and 8 hours post-dose;
 - If it is known upfront that the subject is not available for the ‘full’ PK profiling on Day 15, it is allowed to schedule and perform this PK profiling on Day 29.
- Day 29: pre-dose;
- ED (if applicable): one additional sample to be taken pre-dose if study drug is still taken, or at any time during the visit if study drug is no longer taken.

Plasma concentrations of GLPG2222 will be measured using a validated liquid chromatography tandem mass spectrometry method with a lower limit of quantification of 1.00 ng/mL. The details of sample handling and shipment instructions will be provided in a separate laboratory manual.

After the study is completed, any left-over samples belonging to the study subject may be stored for a period of 5 years under the control of the sponsor. These samples may be used by the sponsor or sponsor’s partner, or by other companies belonging to the sponsor for additional PK investigation (i.e. metabolic profiling, which is the assessment of biochemical intermediates – metabolites - in blood in order to describe the metabolic pathway of the compound). No characterization of human genetic material will be undertaken. Specific consent for storage of samples should be obtained from the subjects. Any research outside the context described in this protocol may only be conducted after approval by the IEC(s)/IRB(s) and Regulatory Authority.

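### No scheduled on-treatment ECG falls near peak exposure: PR, QRS and QT/QTcF are read only at trough, at every dose level

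*Protocol*

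**What the plan says.** Section 6.1 sets the default, "All assessments should be performed pre-dose", and adds that "some assessments are also to be performed at defined time points post-dose when specifically mentioned"; flow chart footnote 1 sets the same rule. For the ECG no such time is mentioned. Flow chart footnote 7 reads "12-lead ECG to be measured after at least 5 minutes of rest in supine position", and section 6.4.5 says "A resting 12-lead ECG will be recorded at the time points specified in the flow chart"; both otherwise give only the resting condition. Section 5.3.3 has the visit-day dose given after the pre-dose assessments.

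Other measures do get a post-dose reading. For vital signs, "Vital signs must be recorded pre-dose at all visits, and additionally between 3 and 4 hours post-dose on Day 1". Spirometry is repeated 1-2 h post-dose on Days 1 and 29. PK blood is drawn over most of a working day: "Day 15: pre-dose and 0.5, 1, 2, 3, 4, 6 and 8 hours post-dose", with the profile movable to Day 29.

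The primary endpoint (section 4.1) covers adverse events "as well as changes over time in weight, vital signs, oxygen saturation by pulse oximetry, 12-lead ECG, spirometry" and laboratory data. SAP section 13.3 turns the ECG part into descriptive, category, shift, worst-case and change tables. The only post-dose time point in SAP section 4.3 is Day 1, for vital signs.

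**The concern.** If a drug effect on cardiac intervals follows plasma concentration, a reading just before the next dose is the least sensitive one in the dosing interval. The protocol itself treats peak exposure as the relevant yardstick: in section 2.2.2 the hERG and dog cardiovascular margins are expressed against C_max.

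The ECG tables are part of the primary endpoint, the QTcF withdrawal criterion in section 5.2.7 draws on the same recordings, and section 2.6.2 says that the results will aid dose selection for combination therapy. Clean tables in the 200 and 400 mg arms could be taken as covering the whole dosing interval, when the schedule samples only its end. The trial also enrols women and doses CF subjects for 29 days. The three earlier clinical studies summarised in section 2.5 enrolled men only, and the one in CF gave single doses to 6 subjects.

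**Working it through.** **Step 1. Trace the schedule.**

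| Assessment | Named post-dose time | Where |
|---|---|---|
| Vital signs | 3-4 h, Day 1 | Footnote 5; section 6.4.3 |
| Spirometry | 1-2 h, Days 1 and 29 | Footnote 8; section 6.3.2 |
| PK blood | 0.5-8 h, Day 15 (or Day 29) | Footnote 13; section 6.5.1 |
| 12-lead ECG | none | Footnote 7; section 6.4.5 |

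ECGs are scheduled at screening and Day 1 (before any drug), Days 15 and 29 (pre-dose), early discontinuation, and follow-up 2 weeks after the last dose. Scheduled on-treatment visit ECGs: 2, both at trough. Scheduled ECGs at a defined post-dose time: 0, at all four doses.

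**Step 2. How far below peak is trough?** The documents give no trough-to-peak ratio, so there is no figure to reproduce. Inputs:

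- Dosing interval 24 h (once daily, section 5.3.3).
- Accumulation 1.5, from section 2.5.1: "Steady state in GLPG2222 plasma concentrations was reached after 2 dosing days with a minimal accumulation (1.5"). These were healthy males on the suspension, and the text does not say which PK parameter the ratio refers to.
- t_max is blacked out. It is assumed to be 2-6 h, within the PK sampling times.
- Model: one compartment, mono-exponential decline after t_max.

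With R = 1/(1 - f), the fraction left after 24 h is f = 1 - 1/1.5 = 1/3. Then k = ln(3)/24 = 0.0458 per h, and the effective half-life is ln(2)/k = 15.1 h.

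Trough/peak = exp(-k(24 - t_max)):

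| t_max | R = 1.3 | R = 1.5 | R = 1.7 |
|---|---|---|---|
| 2 h | 0.26 | 0.37 | 0.44 |
| 4 h | 0.29 | 0.40 | 0.48 |
| 6 h | 0.33 | 0.44 | 0.51 |

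**Step 3. What that does to an effect.** Take, for scale only, an effect of 10 ms at peak that is linear in concentration. It would read 10 x 0.37 = 3.7 ms to 10 x 0.44 = 4.4 ms at trough with R = 1.5, and 2.6 to 5.1 ms over the whole table.

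**Step 4. Late doses.** Section 5.3.3 allows a dose up to 12 h late, so the gap before a visit ECG can shrink to about 12 h. With R = 1.5, exp(-k(12 - t_max)) is 0.63 at t_max 2 h and 0.76 at 6 h: higher, but still below peak.

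**Step 5. Heart rate.** The Day 1 vital signs follow the first dose. In the same model the first-dose peak is 1/R = 1/1.5 = 67% of the steady-state peak, so heart rate is observed at an exposure well above trough. PR, QRS and QT are not.

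**The case against.** The strongest reply is that the prior evidence is reassuring. Section 2.2.2 reports no significant PR, QRS, QT or QTc effect in dogs at 14-fold (females) and 2.6-fold (males) the C_max extrapolated for 450 mg once daily. It also refers to a hERG concentration about 1,000-fold the free C_max, with the result blacked out. Section 2.5.1 reports no clinically significant ECG findings up to 600 mg, above this trial's top dose. This stands, and it keeps the point from being a serious one. It does not close the gap: the clinical data are from healthy men, and the documents do not say when those ECGs were taken relative to dosing.

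It can also be said that the ECG analysis is descriptive, without p-values, in about 10 subjects per arm (25 x 2/5), and that neither document claims cardiac safety at peak. That is true. The point is therefore a limit on what the tables can show, not a contradiction in the plan.

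The figures are open to challenge too. Half-life and t_max are blacked out, and section 2.5.2 says the tablet, used here, is absorbed more slowly than the suspension. That is why t_max is carried to 6 h and the ratio is offered as an illustration.

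Finally, a post-dose ECG has costs. It disturbs the mandatory order in section 6.1, where the ECG precedes sweat collection and spirometry, and it removes the pre-dose ECG check on that day. These objections shape the fix but do not remove the reason for it.

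**Conclusion.** The point holds for scheduled ECGs. PR, QRS and QT/QTcF are planned at trough only, at roughly 37-44% of peak concentration under the stated model, or about a quarter to a half once accumulation is allowed to vary from 1.3 to 1.7. The schedule finding comes directly from the documents. The percentages rest on the one-compartment form, a healthy-male accumulation ratio and an assumed t_max.

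Three stronger readings are tempting but not supported:

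- A reader might infer that no ECG could ever fall near peak. Unscheduled ECGs are possible and enter the worst-case derivation in SAP section 13.3.5, and the early-discontinuation ECG has no fixed relation to dosing once drug is stopped. Neither is a planned near-peak reading.
- A reader might infer that rate effects are missed as well. The Day 1 post-dose vital signs cover heart rate, though only after the first dose.
- A reader might convert the ratio into a dose and say that the 400 mg ECGs reflect the peak of roughly 150 mg (400 x 0.37 = 148). That needs dose-proportional exposure, and section 2.5.1 reports more than proportional exposure over part of its range.

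Nothing in the documents indicates an actual cardiac signal. This is a modest design weakness that is cheap to correct.

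**What to change.** On the full PK-profile day (Day 15, or Day 29 if the profile is moved), take that visit's ECG post-dose, immediately before a PK draw chosen from the sponsor's own tablet t_max data. Keep the other on-treatment ECG and the Day 1 ECG pre-dose.

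In the protocol, name the time in flow chart footnote 7 and section 6.4.5, and amend the order list in section 6.1 so that sweat collection and spirometry stay pre-dose. In SAP section 4.3 and Tables 14.3.3.1 to 14.3.3.5, report the reading as a single post-dose, profile-day time point pooled over Days 15 and 29, as SAP section 10.1.2 already does for the PK profile, and set it against concurrent placebo. Footnote 13 exempts no placebo subjects from the profile, so that comparison should be available.

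The change adds no visit, procedure or ECG, because subjects are already on site to 8 h. Its price is one fewer trough ECG per subject, no pre-dose ECG check on the profile day, and a later, post-meal reading compared with a pre-dose baseline. The placebo group largely controls for the last of these.

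If the schedule is left as it is, state in both documents that ECG conclusions apply to trough exposure only.

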1. CFQ-R
2. Vital signs and pulse oximetry
3. 12-lead ECG
4. Sweat collection
5. Spirometry
6. Sampling for clinical laboratory tests and PK
7. Sampling for exploratory biomarkers
8. Nasal brushings (if applicable)

All other procedures can be performed in any order, unless otherwise stated, as long as they meet the schedule for pre- or post-dose evaluations.

6.2. INITIAL SUBJECT AND DISEASE CHARACTERISTICS

Subjects will be asked to come to the clinical study center for the screening visit, which may be scheduled between 28 days and 1 day prior to baseline (Day 1). The CFQ-R will be completed after informed consent was given by the subject, and prior to any other assessments scheduled for that visit. As part of the safety assessments, vital signs will be recorded, a pulse oximetry will be performed to measure oxygen saturation, and a 12-lead ECG will be recorded. Efficacy assessment tests will be performed, including sweat collection and spirometry. Blood and urine samples will be collected for clinical safety laboratory tests, serology, pregnancy test, and FSH test (if applicable). In addition, the following assessments will be done during screening: a complete check of inclusion and exclusion criteria, demographics (recording of year of birth, age and race), a general medical examination including medical and surgical history (including CF-specific medical history e.g. date of diagnosis, sweat chloride concentration prior to any treatment with a CFTR modulator, CFTR mutation, etc.) and questions about smoking habits, alcohol and drug intake, a full physical examination (including height), and weight. Finally, the subject diary will be dispensed.

All AEs (serious and non-serious) and concomitant medications will be reported continuously from the time a signed and dated ICF is obtained until the final follow-up visit.

6.3. EFFICACY ASSESSMENTS

6.3.1. Sweat Chloride Concentration

Sweat chloride concentration is a biomarker of CFTR ion channel function. It is a sensitive, standardized and non-invasive measure to assess systemic CFTR modulator effects. Chloride concentration will be measured in sweat collected by an approved collection device (Wescor Macrōduct® system) according to the 2009 guidelines issued by the Clinical and Laboratory Standards Institute.

To ensure consistency and reproducibility in this multi-center study, ‘trained’ clinical study centers will collect sweat according to standardized operating procedures. Two sweat collections, one from each arm, will be obtained from each subject at the time points indicated in the flow chart. Sweat samples will immediately be frozen and sent to the central laboratory for testing and interpretation of results.

The clinical study center should be encouraged to select subjects for the study for which it is known that adequate quantities of sweat can be collected.

Clinical study centers and subjects should not be informed of their sweat chloride results during the entire study duration, regardless of whether the subject prematurely discontinues treatment.

6.3.2. Spirometry

Spirometry will be performed to assess pulmonary function at the time points specified in the flow chart. Spirometry must be performed pre-dose at all visits, and additionally between 1 and 2 hours post-dose on Day 1 and Day 29.

The spirometry test must meet the criteria for acceptability and repeatability as defined in the 2005 ATS/ERS guidelines on standardization of lung function testing [7].

If screening spirometry measurements fail to meet acceptability and repeatability criteria in the first 3 efforts, up to 8 repeat spirometry efforts may be performed. If repeat values of the individual assessment(s) satisfy the eligibility criteria and are completed within the screening window, then the subject is eligible for the study.

Clinical study centers will be provided with spiroimeters to be used for all study spirometry assessments. Pulmonary function will be measured in a standardized manner. Spirometry data will be transmitted to a centralized spirometry service for quality review. Subjects should not be informed of their study-related spirometry results during the entire study duration, regardless of whether the subject prematurely discontinues treatment.

At screening, spirometry to determine subject’s eligibility should preferably be performed pre-bronchodilator. If the subject used his/her bronchodilator before the screening visit, screening spirometry is allowed to be performed post-bronchodilator. At all other study visits, spirometry should be performed pre-bronchodilator. If on Day 1, the subject forgets to withhold his/her bronchodilator, all subsequent spirometry testing should be performed post-bronchodilator, to be consistent with the conditions for the baseline measurement. If on Day 1, spirometry is collected pre-bronchodilator, but the subject forgets to withhold his/her

dose of bronchodilator at a subsequent visit, then spirometry should be collected post-bronchodilator for that visit only.

Pre-bronchodilator spirometry is defined as spirometry testing performed for a subject:

- that withheld his/her short-acting β -agonist (e.g. albuterol) or anticholinergic (e.g. ipratropium bromide) for more than 4 hours prior to the spirometry assessment, AND
- that withheld his/her long-acting bronchodilator such as salmeterol or formoterol for at least 12 hours, or longer-acting agents such as indacaterol and tiotropium for at least 24 hours prior to the spirometry assessment.

The following parameters will be measured as part of the spirometry assessment:

- FEV₁ (L) and percent predicted FEV₁ for age, gender, and height;
- Forced vital capacity (FVC) (L) and percent predicted FVC for age, gender, and height;
- FEV₁/FVC ratio;
- Forced expiratory flow between 25% and 75% of exhaled volume (FEF₂₅₋₇₅).

Predicted values will be estimated using the 2012 Global Lungs Initiative equation.

